6.5. Sampling Method

In this study, we will use multistage sampling aligned with the principles of a cluster randomized controlled trial. In the first stage, the clusters are health centers within Addis Ababa that have palliative care services through Family Health Teams. Of the 101 health centers, 95 currently deliver palliative care and will form the sampling frame. A complete list of eligible facilities will be obtained from Addis Ababa regional health bureau. To make sure the selected clusters are representative of the city, we will use stratified random sampling, stratifying facilities by patient volume. After this, these facilities will be randomly allocated to either the intervention or control group using a computer-generated sequence managed by an independent person so that there's allocation concealment. A total of 12 clusters (6 per arm) will be included in the study.

In the second stage, all patients currently diagnosed with a chronic illness and receiving follow-up home-visit care from the Family Health Teams within the selected cluster

catchment areas will be included consecutively. This population forms the denominator for the study's proportion-based primary outcome, representing the total reach of the implementation environment. Given that the screening is integrated into routine clinical care, verbal informed consent will be sought from each identified patient (or their proxy caregiver) for the research use of their data. This verbal consent will be witnessed and documented. The numerator will then be defined as the subset of these chronic patients who are successfully screened and identified for palliative care needs using either the DINKNESH App (intervention) or standard paper-based tools (control). This multistage approach ensures that the study captures real-world implementation fidelity while minimizing selection bias among the target chronic patient population.

For the qualitative component, we'll purposely identify healthcare providers and key stakeholders from facilities assigned to the intervention arm. Participants will be chosen based on their direct involvement in the rollout or oversight of the palliative care App, ensuring diversity across roles. Data will be collected through FGD organized by professional category to foster open dialogue and reduce hierarchical influence. The number of FGDs will be guided by thematic saturation, typically reached after four to six FGDs.

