6.4. Sample Size Determination

The sample size for this cluster randomized trial is determined using standard approaches for cluster-randomized trials with proportion (binary) outcomes, aligned with Hayes and Bennett (1999). This study specifically screens individuals with known chronic conditions, the primary endpoint is evaluated as the proportion of chronic patients identified as requiring palliative care.

The calculation is based on estimating the difference in identification proportions between the intervention and control arms. Based on literature, we estimate the baseline identification proportion of palliative care needs among chronic patients in routine care P1 to be 5% (0.05). We hypothesize that the DINKNESH App will increase systematic identification by a factor of 3, resulting in an expected proportion (P2) of 15% (0.15) in the intervention arm.

To detect this difference with 85% power ($Z_{1-\beta} = 1.04$) and a 5% significance level ($Z_{1-\alpha/2} = 1.96$), we calculated the unadjusted sample size and then applied a Design Effect (DE) to account for facility-level clustering. We estimated an ICC of 0.03, supported by methodological standards for primary care practice-level clustering.

Each cluster is defined as two Family Health Team (FHT). Based on routine service data, two FHT encounters approximately 120 individuals that have underlying chronic conditions over a six-week period. Thus, the expected average cluster size (m) of eligible chronic patients over the six-week study period is 120.

Then, the required design effect is 4.57. Multiplying the unadjusted individual sample size (approximately 157.5 per arm) by this design effect requires approximately 720 chronic patients per arm. Dividing this by the average cluster size ($m = 120$) yields exactly 6 clusters per arm. This results in a total of 12 clusters included in the study. This provides a total expected denominator of 1,440 routine chronic patient encounters over the six-week study period.

$$n = (Z_{1-\alpha/2} + Z_{1-\beta})^2 \times (p_1(1-p_1) + p_2(1-p_2)) \times (1 + (m-1)\rho) / (p_1 - p_2)^2 \times m$$

- ($Z_{1-\beta} = 1.04$) and a 5% significance level ($Z_{1-\alpha/2} = 1.96$)
- Baseline identification proportion (P1): 0.05 (5%)
- Expected identification proportion (P2): 0.15 (15%)
- Difference in proportions: 0.1
- Average chronic patient encounters per cluster (m): 120 (over 6 weeks)
- Design Effect (DE): $1 + (m-1) \times ICC = 1 + (119 \times 0.03) = 4.57$

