6.8. Data Analysis

We will have a mixed-methods design, analyzing quantitative and qualitative data separately and then integrating the findings during interpretation to generate a comprehensive understanding of the DINKNESH App's effectiveness and Implementation.

The primary effectiveness outcome for analysis is defined as the number of patients identified as having palliative care needs by family health teams during routine home visits over 6 weeks study period. This outcome will be operationalized as the number of individuals identified as requiring palliative care divided by the total number of chronic patient encounters conducted within each cluster.

In alignment with the study objectives, quantitative analyses will address the identification of patients with palliative care needs (primary outcome)

Quantitative data will be cleaned up and analyzed using standard statistical software Stata. Models with adjustment for clustering at the facility level will be used. This approach accounts for the clustered study design and enables valid comparison of identification rates between intervention and control arms. The model will test if the DINKNESH App process led to a significantly higher rate of patient identification and documented action compared to the Control arm.

For the Qualitative part, We will analyze the transcripts from the Focus Group Discussions using thematic analysis. This involves systematically reading the transcripts and categorizing recurring quotes and ideas into specific themes. This analysis will tell us the exact process issues that need fixing before the DINKNESH App can be scaled up

nationally.

Findings from quantitative analyses will be triangulated with qualitative insights from healthcare workers and identified patients with palliative care need to contextualize observed differences in identification and clinical action, and to explain how and why the DINKNESH App influenced routine care practices.

7. Ethical Consideration

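### The volume strata used to draw the 12 facilities are not stated to govern their allocation; allocating within them is a cheap improvement.

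*Protocol*

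**What the plan says.** Protocol section 6.5 describes two steps in sequence.

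- Selection. "Of the 101 health centers, 95 currently deliver palliative care and will form the sampling frame". From this frame the facilities are drawn with strata: "To make sure the selected clusters are representative of the city, we will use stratified random sampling, stratifying facilities by patient volume". The one purpose given is representativeness.
- Allocation. The text then continues: "After this, these facilities will be randomly allocated to either the intervention or control group using a computer-generated sequence managed by an independent person". The arm sizes follow: "A total of 12 clusters (6 per arm) will be included in the study".

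The allocation step names no strata, blocks, pairs, minimisation or constraint on volume, and no other section adds one. The number of volume strata, their cut points and the number of facilities per stratum are not stated.

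Section 6.8 describes the primary model only in general terms: "Models with adjustment for clustering at the facility level will be used".

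**The concern.** The plan will already hold volume strata when it randomises, but does not say that they carry over. With six clusters per arm, chance differences between arms in facility type have little room to average out.

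The protocol gives some reason to think that volume could matter. Its justification of the cluster design (section 3) lists variation in workload among the constraints that affect how the intervention performs, and section 4.1 expects workload pressure to be a possible barrier. Facility volume is a natural proxy for workload, although the protocol does not draw that link.

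At stake are precision and the ease of interpretation. If one arm held most of the high-volume facilities, part of an observed difference could be put down to that, and an adjustment chosen afterwards would be open to challenge. Balance has to be built in before the sequence is generated; no later document can restore it.

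**Working it through.** **Inputs from protocol section 6.4:** P1 = 0.05, P2 = 0.15, z = 1.96 and 1.04, ICC = 0.03, m = 120, 6 clusters per arm. **Assumed, because the protocol does not give them:** the strata (two of six, three of four or four of three) and the share R² of between-cluster variance that volume explains (0 to 30%).

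**1. The plan's own sample size.**
- Variance sum: 0.05 × 0.95 + 0.15 × 0.85 = 0.175.
- Unadjusted n: (1.96 + 1.04)² × 0.175 / 0.10² = 157.5 per arm.
- Design effect: 1 + 119 × 0.03 = 4.57.
- 157.5 × 4.57 = 719.8 per arm, and 719.8 / 120 = 5.998, so 6 clusters per arm.

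The stated figures reproduce and are not in dispute here.

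**2. Chance imbalance if the strata are ignored.** There are C(12,6) = 924 equally likely 6:6 allocations. With two strata of six, the number that put k high-volume facilities in the intervention arm is C(6,k)²: 1, 36, 225, 400, 225, 36, 1 for k = 0 to 6.
- Exact 3-3: 400/924 = 43.3%.
- 4-2 or worse: 524/924 = 56.7%. Of these 524 allocations, 450 are 4-2 splits.
- 5-1 or worse: 74/924 = 8.0%.
- Complete separation: 2/924 = 0.2%.

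Full enumeration for other layouts:
- Three strata of four: some imbalance in 76.6%, and at least one stratum wholly in one arm in 14.3%.
- Four strata of three: at least one stratum wholly in one arm in 47.4%.

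**3. What a split could do to the estimate (illustration).** Suppose that the identification proportion differs by 2 to 5 percentage points between high- and low-volume facilities, and that clusters count equally.
- 4-2 split: (4 − 2)/6 × 2 to 5 = 0.7 to 1.7 points.
- 5-1 split: (5 − 1)/6 × 2 to 5 = 1.3 to 3.3 points.

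The planned difference is 10 points.

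**4. Power with and without the stratum.** SE = √(0.175 × DE / 720), the noncentrality is 0.10/SE, and power comes from the noncentral t distribution.
- No stratum term: DE = 4.57, SE = 0.0333, noncentrality 3.00. With 10 df (critical value 2.228) power is 77.2%. The normal approximation used in the plan gives Φ(3.00 − 1.96) = 85.1%.
- The design effect splits into 0.97 within clusters (1 − ICC) and 3.6 between clusters (m × ICC). A balanced stratum term leaves DE = 0.97 + 3.6 × (1 − R²).

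| R² | DE left | Noncentrality | Power, two strata (9 df) |
|---|---|---|---|
| 0% | 4.57 | 3.00 | 76.1% |
| 5% | 4.39 | 3.06 | 77.8% |
| 10% | 4.21 | 3.13 | 79.4% |
| 20% | 3.85 | 3.27 | 82.8% |
| 30% | 3.49 | 3.43 | 86.2% |

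Against 77.2%, the change runs from a loss of about 1 point to a gain of about 9 points, and breaks even somewhere between R² = 0 and 5%. With three strata (8 df, critical value 2.306) the same formula gives 74.8%, 78.1%, 81.6% and 85.1% for R² of 0, 10%, 20% and 30%.

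**5. After the change.** With two strata of six, every allocation is 3-3, and C(6,3)² = 400 allocations remain. With three strata of four, every allocation is 2-2, and C(4,2)³ = 216 remain. N stays at 12 clusters and 1,440 patients. Strata of three cannot split evenly; 2-1 is the best available.

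**The case against.** The strongest objection is that the protocol is silent rather than wrong. A reader might infer that it prescribes an unrestricted sequence, but the text does not say that: a computer-generated sequence can be stratified, and the allocation sentence follows directly on the stratification sentence. This stands. What remains is that simple randomisation would also comply, and the choice has to be settled before randomisation.

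A reader might also infer that the plan treats volume as prognostic. It does not: the only stated purpose is a representative sample. The workload remarks make a link plausible but do not establish one. Section 6.4 also defines each cluster as two Family Health Teams with about 120 eligible patients expected, so facility volume need not carry through to the analysed cluster size, and the outcome is a proportion, which volume does not raise mechanically.

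A third tempting reading is that the arms are likely to differ badly. The figures do not support it for two strata: most of the 57% is the mildest possible departure from balance, and the serious splits make up 8%. The allocation remains a valid randomisation either way.

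The power gain depends on an R² for which the documents offer no value; at 5% it is only 0.6 points. Finally, model covariates are commonly left to a statistical analysis plan, so the lack of a stratum term in section 6.8 is not itself a fault.

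**Conclusion.** The point holds as a cheap improvement, not as an error or contradiction. Section 6.5 forms volume strata for sampling and leaves open whether they restrict the allocation. If they do not, and there are two strata of six, some imbalance is more likely than not (57%), usually mild, with an 8% chance of a 5-1 split or worse. With three strata of four, the chance of some imbalance is 77%.

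The consequence is chance imbalance and lost precision. The size of the benefit rests on three assumptions: the layout of the strata, a relation between volume and identification, and the share of between-cluster variance that it explains. The imbalance probabilities need only the first of these.

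**What to change.** In section 6.5, state that the independent person allocates facilities 1:1 within the volume strata already formed. Give the number of strata and their cut points, and define them so that each holds an even number of selected facilities, for example two of six or three of four. State, there or in the statistical analysis plan, that the stratum enters the primary model as a fixed effect. Stratifying the allocation without that term would leave the variation due to volume in the standard error.

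The number of clusters and patients does not change. The costs are one degree of freedom with two strata (about 1 point of power if volume is irrelevant) or two with three strata (77.2 − 74.8 = 2.4 points), and a small constraint on the sampling step, since a strictly proportional draw of 12 from 95 may give odd numbers per stratum. The change must be made before the sequence is generated.

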6.6. Data Collection

We will use a mixed method to collect both quantitative and qualitative data, ensuring a comprehensive evaluation of the DINKNESH App's impact. For the quantitative part, data will be extracted from the DINKNESH app backend logs in the intervention arm and paper-based forms in the control arm, measuring the health care workers' documented patient identification rates and clinical action taken. All data collectors will be trained appropriately to ensure ethical conduct and will conduct weekly site visits to document the number of chronic patients visited and screened, ensure data integrity and adherence to the study protocol across all eight clusters.

For the qualitative component, we will conduct FGDs with health care workers

purposely selected from the intervention arm. This purposive identification is designed to ensure maximum variation in experience and professional role to gather both hands-on user experiences and health facility insights. The FGDs will explore user experiences, perceived usability of the App, and contextual enablers and barriers (systemic, human, and technological) affecting the App's integration into routine workflows. In depth interviews will also be made in selected identified patients in both intervention and control to compare their experiences. All discussions will be audio-recorded with consent, transcribed verbatim, and translated from Amharic into English by experienced translators.

6.7. Data Management

All data will be managed with strict attention to confidentiality. Data generated by the DINKNESH App (Intervention Arm) will be automatically uploaded to a cloud server accessible only to the core research team. In the control arm, data will be recorded on standardized paper logs. Prior to analysis, data cleaning will be standardized across both arms, including automated range checks, consistency reviews, and manual outlier detection. Each participant and facility will be assigned a unique study ID to maintain anonymity throughout.

Qualitative data from Focus Group Discussions will be audio recorded, transcribed verbatim, and checked against recordings for accuracy. Transcripts will be de-identified immediately upon transcription and imported into qualitative analysis software for systematic coding.

All data, whether quantitative or qualitative, will be securely stored, regularly backed up, and retained in line with institutional data protection protocols.

6.8. Data Analysis

We will have a mixed-methods design, analyzing quantitative and qualitative data separately and then integrating the findings during interpretation to generate a comprehensive understanding of the DINKNESH App's effectiveness and Implementation.

The primary effectiveness outcome for analysis is defined as the number of patients identified as having palliative care needs by family health teams during routine home visits over 6 weeks study period. This outcome will be operationalized as the number of individuals identified as requiring palliative care divided by the total number of chronic patient encounters conducted within each cluster.

In alignment with the study objectives, quantitative analyses will address the identification of patients with palliative care needs (primary outcome)

Quantitative data will be cleaned up and analyzed using standard statistical software Stata. Models with adjustment for clustering at the facility level will be used. This approach accounts for the clustered study design and enables valid comparison of identification rates between intervention and control arms. The model will test if the DINKNESH App process led to a significantly higher rate of patient identification and documented action compared to the Control arm.

For the Qualitative part, We will analyze the transcripts from the Focus Group Discussions using thematic analysis. This involves systematically reading the transcripts and categorizing recurring quotes and ideas into specific themes. This analysis will tell us the exact process issues that need fixing before the DINKNESH App can be scaled up

nationally.

Findings from quantitative analyses will be triangulated with qualitative insights from healthcare workers and identified patients with palliative care need to contextualize observed differences in identification and clinical action, and to explain how and why the DINKNESH App influenced routine care practices.

7. Ethical Consideration

Ethical approval for this study will be obtained from the Research Review Ethics Committee of Addis Ababa University, College of Health Sciences. In addition, an official support letter will be secured from the Addis Ababa City Administration Health Bureau (AAHB). To ensure full institutional accountability and successful implementation, administrative permission will be obtained from the respective sub city health office heads and the facility managers of the 12 selected health centers. These stakeholders will be engaged throughout the process to ensure the study aligns with facility-level workflows and regional health priorities.

Before data collection, all participants will be fully informed about the study's purpose, procedures, potential risks, and benefits. Written informed consent will be obtained from all Health Care Workers and formal verbal informed consent will be obtained from all eligible chronic patients prior to the screening process. For patients who are unable to provide consent due to their clinical condition, proxy consent will be obtained from their primary caregiver. Participation will be entirely voluntary, and individuals will have the right to withdraw from the study at any stage without any negative consequences or loss of standard care benefits.

Confidentiality will be strictly maintained throughout the study. No personal identifiers will be collected or linked to the data. Each participant and facility will be assigned a unique study code to ensure anonymity. Given the use of an mHealth application, enhanced security measures will be implemented. All data including App backend logs, Audio recordings will be encrypted, password-protected, and stored securely on a server accessible only to authorized members of the research team. Audio recordings from Focus Group Discussions and in depth Interview will be transcribed, anonymized immediately, and stored securely, with identifying information removed to protect participant privacy.

All ethical principles outlined by Addis Ababa University and the Addis Ababa City Health Bureau will be rigorously followed to ensure respect for participants, data integrity, and institutional accountability

8. Dissemination of Result

The findings of this study will be submitted and presented to Addis Ababa University. The results will also be conveyed to the health office accountable, stakeholders, and health centers. An effort would be made to present it at various seminars, research conferences, and workshops. Finally, an attempt will be made to publish it in high impact journals. The study findings will be given to the Addis Ababa Health Bureau, as well as other relevant stakeholders.

9. Work Plan

[illegible]

[illegible]

Table 1: Work Plan

11. Budget Plan

No	Expenses	Measurement in Units/No.	Unit Price (ETB)	Total (ETB)
I. LOGISTICS + PERSONNEL COSTS FOR TRAINING				
1.	Compensation for Trainers	4 Trainers	1500/person/day For 3 days	18,000
2.	Venue + Daily Refreshments & Catering	24 HCW - 2HCW per health center - 24 HCW for 2 days and - 12 HCW for 3 days 4 trainer Total = 28 People - 28 people for 2 days	900/person/day For 3 days	64,800

		- 16 people for the 3rd day		
3.	Compensation for Trainee	24 HCW 2HCW per health center 24 HCW for 2 days and 12 HCW for day 3	600/person /day For 2 days - for 24 people 600/person /3rd day for 12 people	36,000
4.	Stationary(Photocopying & Tool Printing) and Supplies	Patient Consents,and other Notebooks, Pens, Batteries, Audio Recording	-	5,000
5.	Tablets	2 * 6 Tablets = 12 Tablets (2 Tablets per Health center)	- (will use existing DINKNES H tablets)	-
6.	Software Support Team Compensation	2 Team Members	For 3 months	12,000
II. DATA COLLECTION				

7.	SIM Card Purchase	12 SIM Cards	100/per SIM Card	1,200
8.	Internet Package for 2 months	12 Packages	400/per month For 2 months	9600
9.	Local Transportation (PI Supervision)	5 * 6 HC (Every 2 weeks in between monitoring) = 30 Trip within 2 months - Intervention Group	200/trip For 2 months	12,000
		5 * 6 HC (Every 2 weeks - in between monitoring) = 30 Trip within 2 months - Control Group	200/trip For 2 months	
10.	Local Transportation (Data Collector/ Quantitative)	9 * 6 Trips (Weekly Data Collection)= 54 trip within 2 months - Intervention Group	200 /trip For 2 months	21,600
		9* 6 Trips(Weekly data collection) = 54 Trip within 2 months - Control Group	200/trip For 2 months	

11.	Local transportation for X amount of indepth interview in identified patient houses for PI and Qualitative Data collector	2* X Trips	- For 1 month	5,000
12.	Data Collector/ Facilitator Payment	Quantitative Data collection+ Qualitative Data Collection for 2 month	5000/month For 2 months	10,000

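### Section 6.8 divides individuals identified by encounters, while 6.4 and 6.5 plan a proportion of patients; the two agree only if each patient is counted once

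*Protocol*

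**What the plan says.** The protocol describes the primary outcome and its denominator in several places, and the counting unit changes between them.

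- **6.8 Data Analysis.** The outcome is first a count, the "number of patients identified as having palliative care needs by family health teams during routine home visits over 6 weeks study period". The next sentence turns it into a ratio, the "number of individuals identified as requiring palliative care divided by the total number of chronic patient encounters conducted within each cluster".
- **6.4 Sample Size Determination.** Here "the primary endpoint is evaluated as the proportion of chronic patients identified as requiring palliative care". The cluster size rests on routine data in which "two FHT encounters approximately 120 individuals that have underlying chronic conditions over a six-week period". The list of inputs gives the same 120 as an average number of encounters per cluster. The requirement of about 720 patients per arm becomes a "total expected denominator of 1,440 routine chronic patient encounters over the six-week study period".
- **6.5 Sampling Method.** Chronic patients under home-visit follow-up are included consecutively. "This population forms the denominator for the study's proportion-based primary outcome", and the numerator is the "subset of these chronic patients who are successfully screened and identified for palliative care needs".
- **6.6 Data Collection.** Data collectors go to the sites weekly to "document the number of chronic patients visited and screened".

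Nothing in the protocol says that a patient counts once, that only a first visit counts, or how repeat home visits are handled. It gives no number of visits per patient over the six weeks.

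**The concern.** In the 6.8 ratio a person can enter the numerator once but the denominator at every visit. Once anyone is visited twice, the ratio is no longer a proportion of patients and no longer estimates the 5% and 15% on which the trial was sized.

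Repeat visits are plausible, because the inclusion criteria require patients to be receiving home-based follow-up. The visit count also need not be the same in the two arms:

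- The literature review (section 3) cites mHealth evidence of better documentation and follow-up, which would enlarge the app arm's denominator.
- The same section warns that the app may be felt as extra work, which could reduce visits and shrink that denominator.
- Encounters come from app logs in one arm and paper forms in the other, so repeat visits could be recorded differently even if visiting is equal.

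Adjusting for clustering by facility, as 6.8 plans, removes none of this, because the difference would lie between arms.

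**Working it through.** **1. Reproduce the planned sample size.** Inputs from 6.4: p1 = 0.05, p2 = 0.15, z values 1.96 and 1.04, ICC 0.03, m = 120.

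- Unadjusted n per arm = (1.96 + 1.04)² × (0.05 × 0.95 + 0.15 × 0.85) / 0.10² = 9 × 0.175 / 0.01 = 157.5.
- Design effect = 1 + 119 × 0.03 = 4.57.
- 157.5 × 4.57 = 719.8 per arm; 719.8 / 120 = 5.998, so 6 clusters per arm and N = 1,440.

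The plan's figure reproduces. The formula is for a binary outcome per patient, so it supports the 6.4 and 6.5 definition.

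**2. Effect of repeat visits on the 6.8 ratio.** Let v be the mean encounters per patient in six weeks. The protocol gives no value, so every v below is an assumption. Taking the proportion of patients ever identified as fixed:

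- 6.8 ratio in an arm = patient proportion / v.
- Observed ratio between arms = true ratio × (v control / v app).

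Same v in both arms, true 15% vs 5%:

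| v | App | Control | Difference (points) | Ratio |
|---|---|---|---|---|
| 1 | 15.0% | 5.0% | 10.0 | 3.0 |
| 1.5 | 10.0% | 3.3% | 6.7 | 3.0 |
| 2 | 7.5% | 2.5% | 5.0 | 3.0 |
| 3 | 5.0% | 1.7% | 3.3 | 3.0 |

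Different v:

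| v app | v control | True ratio 3.0 appears as | True ratio 1.0 appears as |
|---|---|---|---|
| 1.5 | 1.2 | 2.4 | 0.80 |
| 1.5 | 1.0 | 2.0 | 0.67 |
| 1.0 | 1.2 | 3.6 | 1.2 |
| 1.0 | 1.5 | 4.5 | 1.5 |

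For the first row: 0.15 / 1.5 = 10.0%, 0.05 / 1.2 = 4.17%, ratio 2.4.

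**3. Effect on power if 120 counts visits.** Distinct patients per cluster are then 120 / v. With 6 clusters per arm, effective n per arm = 6 × (120/v) / [1 + (120/v − 1) × 0.03], and power = Φ(0.10 / √(0.175 / effective n) − 1.96).

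| v | Patients per cluster | Design effect | Effective n per arm | Power |
|---|---|---|---|---|
| 1 | 120 | 4.57 | 157.5 | 85.1% |
| 1.5 | 80 | 3.37 | 142.4 | 81.4% |
| 2 | 60 | 2.77 | 130.0 | 77.8% |
| 3 | 40 | 2.17 | 110.6 | 71.0% |

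The loss is modest because smaller clusters also have a smaller design effect.

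**The case against.** The strongest reply is that encounters is loose wording for patients encountered. Section 6.3.2 defines the study population as patients whom the health workers encounter. Section 6.4 uses the word as a verb with individuals as its object, and its arithmetic turns 720 patients per arm into 1,440 encounters, one for one. Sections 5.2, 6.5 and 6.6 all speak of patients. On that reading a patient-level proportion is intended throughout and 6.8 is a slip. It is also fair to say that the opening count in 6.8 is not a serious rival definition, since the next sentence replaces it with the ratio.

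This reading may well be what the authors mean, and it limits what can be claimed. It does not settle the matter: 6.8 is the section that defines the outcome for analysis, and its wording names a different denominator.

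A reader might go further and infer that the design is biased, or that it works against the app because identified patients are revisited. The documents do not support that. They give no visit frequency, no revisit schedule and no link between identification and further visits. Equal repeat visiting leaves the ratio at 3.0, and unequal visiting can favour either arm.

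**Conclusion.** The contradiction stands: 6.8 sets a person-over-encounter ratio, and 6.4 and 6.5 set a proportion of patients. Its consequence is conditional. If each patient is seen once, there is none. If patients are seen more than once equally often in both arms, the proportions and their difference shrink by the factor v and the ratio is unaffected. If visits, or their logging, differ between arms, the ratio is multiplied by control visits over app visits. In the scenarios shown, a true null would appear as anything from 0.67 to 1.5.

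The sample size arithmetic is correct, and it would be wrong to infer that the trial is shown to be underpowered. The planned power of 85% holds if 120 counts distinct patients, which the word individuals in 6.4 implies. Only if 120 counts visits does power fall, to about 81% at 1.5 visits per patient and 78% at 2, with the ICC of 0.03 and the 5% and 15% unchanged.

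This should be settled before data collection. Section 7 states that no personal identifiers will be collected, so repeat visits can be recognised only if the study ID is set up for that purpose.

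**What to change.** - **Definition.** In 6.8, and in the same words in 6.4, state the outcome on the patient basis of 6.5: distinct eligible chronic patients identified at least once in the six weeks, divided by distinct eligible chronic patients visited at least once, per cluster. Restricting the denominator to patients visited agrees with the study population in 6.3.2; say so in 6.5, which could be read as everyone under follow-up.
- **Counting.** Assign the study ID of 6.7 at a patient's first visit and reuse it at every later visit, in both the app and the paper logs. Do not add up the weekly tallies of 6.6 where the same patient may recur.
- **Sample size.** Confirm from the routine service data that 120 counts distinct patients. Only then replace 1,440 encounters with 1,440 patients. If 120 counts visits, restate N and power.
- **Encounters.** Report them by arm as a descriptive measure of workload only.

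The cost is a few sentences, de-duplication by study ID, and discipline in using the ID on the paper logs, which is the harder part.
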